1.2 STUDY RATIONALE

This clinical study has been designed to investigate the effect on MCC of the new HFA-152a propellant in comparison with the marketed HFA-134a propellant, by measuring the clearance from the lungs of inhaled radioaerosol.

This study was conceived in accordance with the guidelines on orally inhaled products (OIP), specifying that "it may be necessary to assess any effect that the new propellant or excipient may have on mucociliary clearance" [14].

MCC is an effective mechanism operating in the lungs to clear the airways of mucus, of inhaled infectious and toxic particles, and of locally-produced biological debris [15]. This mechanism consists of secretory and ciliated cells that beat with coordination and generate a propulsive force, which mobilises the mucus blanket toward the larynx for elimination [16]. MCC is affected by a variety of factors, including lung diseases and pharmacologic agents [17]. Its deterioration is associated with a reduction in the protective role of the ciliated epithelium and, in such cases, cough and adequate airflow become critical mechanisms for airway clearance [16].

Considering that pMDI devices represent one of the most commonly used devices for inhaled drug delivery in the treatment of chronic respiratory diseases, it was considered important to investigate the effect on MCC of the new HFA-152a propellant in comparison with the marketed HFA-134a propellant. As this residual risk was deemed not adequately covered by the clinical development

Clinical Study Code No.: CLI-05993AB6-06	Version No.: 1.0	Date: 16 February 2023
EudraCT number: 2022-003247-97		

program, and as it cannot be predicted by *in-vitro* data, this appropriately designed clinical study will adequately address this residual risk.

This open-label, randomised, controlled, 2-way cross-over study will be conducted in male and female adult (aged 18 to 55 years old [inclusive]) healthy volunteers.

Each subject will be administered multiple doses (5 inhalations twice daily [BID] for 8 consecutive days) of each of the two following treatments, according to an order pre-specified by the randomisation list:

- **Test treatment:** placebo HFA-152a propellant via pMDI;
- **Reference treatment:** placebo HFA-134a propellant via pMDI.

The selected treatment dose (i.e. 5 inhalations BID) corresponds to the maximum total daily dose of HFA-134a propellant allowed for administration with the Clenil pMDI device, according to the current summary of product characteristics (SmPC) (for Clenil 100 µg, the maximum allowed daily dose is 1000 µg, administered as 500 µg BID).

The effect on MCC of each propellant will be evaluated by the change, from baseline (before administration of each propellant) to the end of the 8-day treatment period, in the percent particle retention (PPR) evaluated at 0 (immediately), 2 and 4 hours after the administration of a radiotracer.

1.3 RISK/BENEFIT ASSESSMENT

1.3.1 RISK EVALUATION

The toxicological properties of HFA-152a are well-known in industrial applications and indicate a relatively low risk profile. Short-term inhalation of HFA-152a with light exercise did not have exposure effects in human subjects [12]. A comprehensive package of toxicology studies was conducted for the HFA-152a propellant alone, in conformance with the International Council for Harmonisation Technical Requirements for Pharmaceuticals for Human Use (ICH) M3(R2) requirements; results were described in the Investigator's Brochure for CHF 5993 pMDI HFA-152a. The pre-clinical studies did not elicit any findings that could not be attributed to the expected pharmacological action of the test items, and were similar to those previously reported with the formulation of CHF 5993 HFA-134a propellant. It was therefore considered that the change of the propellant to HFA-152a had not produced any new effects. Of particular note, the results of bacterial mutagenicity, *in-vitro* micronucleus, and *in-vivo* micronucleus assays did not show HFA-152a to be mutagenic or genotoxic. However, the results of the embryofoetal toxicology study in rats were not available at the time of the study. Thus, considering the recommendations related to contraception and pregnancy testing in clinical trials from the Clinical Trial Facilitation and Coordination Group [18], the worst-case scenario was considered, i.e. "Demonstrated or suspected human teratogenicity/fetotoxicity in early pregnancy" and contraception measures were taken accordingly.

This study will involve the subjects' exposure to ionising radiation, due to the administration of a radiotracer and the performance of a transmission scan (see Section 7.2.1). Long-term exposure (years or decades) to ionising radiation can cause cancer. The risk of developing cancer as a consequence of taking part in this study is less than 0.01%, which is considered as negligible risk (for comparison, in the general population, the natural lifetime cancer incidence is around 50%) [19], [20]. The radiation dosimetry for this study is summarised in Table 1 below. The radiotracer technetium-99m (99mTc) albumin colloid will be used in this study. Each subject will receive a maximum of 4 administrations of 99mTc-albumin throughout the course of the study, with a target dose of 1-2 MBq per administration (see Table 1). Transmission scan will be performed once during the study, using a planar 57-Cobalt (Co-57) sheet source which has a total effective dose of 0.07 mSv

Clinical Study Code No.: CLI-05993AB6-06	Version No.: 1.0	Date: 16 February 2023
EudraCT number: 2022-003247-97		

per scan. The radiation dose to be administered in this study has been reviewed by the appointed Medical Physics Expert and Clinical Radiation Expert, in line with current regulations. As a precautionary measure, subjects with a historical exposure (5 mSv in the last 12 months or 10 mSv in the last 5 years) or a total dosimetry value which contraindicates their participation will not be allowed in this study (see [Section 4.3](#), exclusion criteria #18 and #19). Each subject will receive a maximum total ionising radiation exposure of 0.27 mSv. This is equivalent to approximately 1 month of average natural background radiation dose in the United Kingdom (UK) or around 14 chest posteroanterior x-ray examinations.

Table 1. Radiation dosimetry of the study

Procedure	Radioactivity per administration	Number of administration	A Total Dose (MBq)	B Effective Dose per administration (mSv)	Total Effective Dose (A x B)
Co-57 transmission scan	-	1	-	-	0.07 mSv
Inhalation of 99mTc- albumin colloid	1-2 MBq	4	8 MBq (maximum 2 MBq per administration)	0.05 mSv	0.2 mSv

99mTC= Technetium-99m; Co-57=57-Cobalt.

The study will be conducted in healthy volunteers. The study population is free of ciliary dysfunction and free of any inhaled medications, and therefore is considered as sensitive for the assessment of the impact of the new HFA-152a propellant on MCC function. Moreover, MCC has been shown to be altered in (healthy) smokers [21],[22]. Therefore, only non-smoker subjects will be included. The subjects will be closely monitored and evaluated by the Investigator during the entire duration of the study. Therefore, the overall risk/benefit assessment for the proposed study is considered to be acceptable.

This study will be conducted in compliance with the Declaration of Helsinki (1964 and amendments), current Good Clinical Practice (GCP) ICH E6 and all other applicable laws and regulations.

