 - a. Women of non-childbearing potential (WONCBP) defined as physiologically incapable of becoming pregnant (i.e. post-menopausal or permanently sterile, as per definitions given in [Appendix 2](#) and in Section 4.1 of the Clinical Trials Facilitation and Coordination Group guidance). Tubal ligation or partial surgical interventions are not acceptable. If indicated, as per Investigator's request, post-menopausal status may be confirmed by follicle-stimulating hormone (FSH) levels (according to local laboratory ranges);

Clinical Study Code No.: CLI-05993AB6-06

Version No.: 1.0

Date: 16 February 2023

EudraCT number: 2022-003247-97

- b. Women of childbearing potential (WOCBP) fulfilling one of the following criteria:
- WOCBP with fertile male partners: they and/or their partner must be willing to use a highly effective birth control method preferably with low user dependency, from the signature of the informed consent form (ICF) and until the follow-up call or;
 - WOCBP with non-fertile male partners (contraception is not required in this case).

Note: In case of hormonal contraception, an additional non-hormonal method (barrier method, preferably male condom) is required.

11. Male subjects fulfilling one of the following criteria:

- Fertile male subjects with a pregnant or non-pregnant WOCBP partner: they must be willing to use male condom, from the signature of the ICF until the follow-up call or;
- Non-fertile male subjects (contraception is not required in this case) or;
- Fertile male subjects with a WONCBP partner (contraception is not required in this case).

For the definition of WOCBP, fertile men and the list of highly effective birth control methods, refer to [Appendix 2](#) or to Section 4.1 of the Clinical Trials Facilitation and Coordination Group guidance.

Inclusion criterion #6 will be re-checked before randomisation.

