7.1.2.1.1 DAY -1 OF TREATMENT PERIOD 1 (V2)

V2 is the first visit of the Investigational Phase and of TP1. It takes place 2 to 21 days after the screening visit.

The following procedures will take place at this ambulatory visit:

- Subject selection: some of the inclusion and exclusion criteria will be re-checked (see [Section 4.2](#) and [Section 4.3](#), respectively). Subjects not fulfilling the inclusion criteria or meeting any of the exclusion criteria will be recorded as screening failures;
- Study restrictions: study restriction criteria and adherence to the wash-out requirements applicable before the MCC assessment will be checked, according to [Section 4.4](#);
- Alcohol breath test: will be performed using a specific kit;
- Concomitant medications: concomitant medications taken by the subject since the screening visit and during V2 will be checked and recorded;
- Urine test: urine samples will be collected for urine cotinine and drug panel test, according to [Section 7.2.6](#);
- Pregnancy test: urine samples will be collected from female subjects for pregnancy testing, according to [Section 7.2.6](#);
- Body temperature: will be assessed according to [Section 7.2.3](#);
- AE recording: the status of AEs ongoing at the screening visit will be checked and updated in the eCRF when applicable. Any new AE occurring since the previous visit will be checked and recorded in the eCRF, as well as the related concomitant medications. Any AE occurring during the study visit must also be monitored and recorded in the eCRF;
- MCC assessment: a Co-57 transmission scan and a background scan will be performed to provide an outline of the lungs. Subjects will then be administered a radiotracer. Image acquisitions for the assessment of MCC will be performed at 0 (immediately), 15 minutes, 30 minutes, 1 hour, 1 hour 30 minutes, 2 hours, 2 hours 30 minutes, 3 hours and 4 hours after the administration of the radiotracer, according to [Section 7.2.1](#).

Clinical Study Code No.: CLI-05993AB6-06

Version No.: 1.0

Date: 16 February 2023

EudraCT number: 2022-003247-97

Before discharge, subjects will be given the following instructions:

- To adhere to the study restrictions and to the pre-spirometry wash-out requirements before coming to V3, according to [Section 4.4](#);
- To avoid taking any of the non-permitted concomitant medications, according to [Section 5.2](#).

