7.1.2.1.2 DAY 1 OF TREATMENT PERIOD 1 (V3)

V3 is the second visit of TP1 and takes place in the morning of the day after V2.

The following schedule will be followed during this ambulatory visit:

- Subjects will undergo the necessary assessments and checks to confirm their eligibility;
- Eligible subjects will be randomised;
- Randomised subjects will undergo the pre-dose assessments;
- Subjects will receive the first dose of one of the study treatments (HFA-152a or HFA-134a, according to their randomisation arm);
- Subjects will undergo the post-dose assessments;
- Subjects will be given the necessary instructions before discharge.

The following procedures and assessments will take place:

- Subject selection: specific inclusion and exclusion criteria will be re-checked (see [Section 4.2](#) and [Section 4.3](#), respectively). Subjects not fulfilling the inclusion criteria or meeting any of the exclusion criteria will be recorded as screening failures;
- Randomisation: subjects will be randomised according to [Section 6.5](#);
- Study restrictions: study restriction criteria and adherence to the wash-out requirements applicable before the spirometry assessment will be checked, according to [Section 4.4](#);
- Concomitant medications: concomitant medications taken by the subject since the previous visit and during V3 will be checked and recorded;
- AE recording: the status of AEs ongoing at V2 will be checked and updated in the eCRF when applicable. Any new AE occurring since the previous visit will be checked and recorded in the eCRF, as well as the related concomitant medications. Any AE occurring during this study visit must also be monitored and recorded in the eCRF;
- Physical examination: a full physical examination will be performed, and any new CS abnormality revealed since the screening visit (V1) will be recorded as an AE;
- 12-lead ECG: a single ECG will be recorded to assess ECG parameters (HR, PR, QRS and QTcF), according to [Section 7.2.4](#). The assessment will be performed before or after the vital signs assessment, in pre-dose: within 1 hour before the intake of the first inhalation of the propellant; and in post-dose: 5 minutes, 15 minutes, 1 hour 45 minutes after the intake of the last inhalation of the propellant;

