7.2 STUDY ASSESSMENTS AND PROCEDURES

7.2.1 MUCOCILIARY CLEARANCE ASSESSMENT

Image acquisitions for MCC assessments, the transmission scan and the background scan will be performed at the timepoints specified in [Table 2](#).

On Day -1 of TP1 (before the assessment of MCC), the gamma scintigraphy procedure will be performed and will consist of a single transmission scan of the thorax, performed using a planar Co-57 source. The procedure will provide an outline of the lungs for use in subsequent analysis. A single background scan will also be performed during this visit, to account for background radiation. Subjects will be standing in front of the camera and any radioactive substance (except the markers) will be removed from the room.

On each visit with MCC assessments (see [Table 2](#)), subjects will be administered 99mTc-albumin colloid via a standardised aerosol delivery procedure. Controlled breathing conditions will be implemented using a metronome and commercial visual flow signal. A Mini 900 Ratemeter will be used to target a dose of 1-2 MBq (maximal dose of 2 MBq per administration). To assure that this adequate dose is achieved, the probe will be shielded with approximately 1 mm lead and will be taken from the middle of a subject's back. Inhalation time will vary by subject size and deposition efficiency, but is expected to be around 2 minutes per subject.

Gamma scintigraphy imaging will be performed over 240 minutes. Image acquisition will begin after completing the 99mTc-albumin administration, and the analysis of these images will provide a measurement of MCC. Anterior and posterior images of a 2-minute duration will be taken at 0 (immediately), 15 minutes, 30 minutes, 1 hour, 1 hour 30 minutes, 2 hours, 2 hours 30 minutes, 3 hours and 4 hours after the administration of the radiotracer. In order to allow accurate alignment of sequential images, an external anatomical marker containing a maximum of 0.02 MBq 99mTc will be taped to the subjects' chest and back, for the duration of the imaging procedures.

On Day 8 of each treatment period, the radiotracer will be administered post-dose, approximately 2 hours after administration of the last dose of the propellant.

Images will be reviewed and counts in each region of interest will be captured and corrected for background and radiation decay. To assess central *versus* peripheral deposition, the lung will be divided into central and peripheral (the area outside central) regions.

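### Could rescreening a subject who fails eligibility after the V2 tracer break the stated ceiling of 4 administrations and 0.27 mSv?

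*Protocol*

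**What the plan says.** **The ceiling.** Protocol Section 1.3.1 limits the tracer: "Each subject will receive a maximum of 4 administrations of 99mTc-albumin throughout the course of the study". It limits the scan as well: "Transmission scan will be performed once during the study". It then gives the total: "Each subject will receive a maximum total ionising radiation exposure of 0.27 mSv". Table 1 shows the components. Section 7.2.1 agrees on the scan, since the Day -1 procedure in period 1 "will consist of a single transmission scan of the thorax, performed using a planar Co-57 source".

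**The order of events.** At V2 (Section 7.1.2.1.1) the scan comes first and "Subjects will then be administered a radiotracer". V3 is the next morning (Section 7.1.2.1.2), where "Subjects will undergo the necessary assessments and checks to confirm their eligibility" before randomisation. Section 4.2 adds that "Inclusion criterion #6 will be re-checked before randomisation". A subject who fails at V3 is recorded as a screening failure.

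**Rescreening.** Section 4.6 defines a screen failure as someone who consented but was not randomised. It permits one rescreening when the Investigator considers the cause temporary. Section 6.5 repeats the permission for failures up to randomisation and bars only drop-outs from being screened again. The timing of V2 is tied to screening: "It takes place 2 to 21 days after the screening visit".

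**Dose safeguards.** Exclusion criterion 18 works at 5 mSv in 12 months and 10 mSv in 5 years. Criterion 19 is a judgement on total dosimetry. Section 14 sends the dosimetry to the radiation advisory committee.

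**The concern.** A figure called a maximum should hold under every path the protocol allows, and here one path appears to exceed it. The tracer is given before eligibility is settled. The V3 check has substance: it includes the first physical examination since V1, and infection, COVID-19 and non-permitted medication are among the criteria re-checked before randomisation. A subject who develops an infection overnight after V2 would be a screen failure with a temporary cause, which is the situation rescreening is meant for. The old V2 could not follow a new screening visit within the stated window, so re-entry seems to require a second V2 and a fifth tracer dose.

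The stake is the risk statement made for healthy volunteers, who gain no benefit from taking part, and the dosimetry put forward for approval. There is also a possible stake for the data. If the limit of 4 prevailed after re-entry, 3 administrations would remain for the 4 scheduled MCC assessments.

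**Working it through.** **Inputs** (Protocol Section 1.3.1 and Table 1): 0.07 mSv per Co-57 scan; 0.05 mSv per tracer administration; at most 2 MBq per administration. Table 2 schedules tracer at V2, V4, V5 and V7, and the scan at V2 of period 1 only. The screening visit V1 involves neither.

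**Formula.** Total dose = (administrations × 0.05) + (scans × 0.07) mSv. Maximum activity = administrations × 2 MBq.

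**The plan's own figure.** One pass: 4 × 0.05 + 1 × 0.07 = 0.20 + 0.07 = 0.27 mSv, and 4 × 2 = 8 MBq. Both match the protocol. The A × B heading in Table 1 is a labelling slip: 8 MBq × 0.05 would be 0.40, whereas the printed 0.2 mSv is 4 administrations × 0.05 mSv. The printed value is right.

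**Failure at V3 without re-entry.** 1 × 0.05 + 1 × 0.07 = 0.12 mSv, below the ceiling.

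**Failure at V3, one rescreening, full completion:**

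| Reading of Section 1.3.1 | Tracer | Scans | Activity | Dose | Excess over 0.27 | Share of 5 mSv |
|---|---|---|---|---|---|---|
| Both limits bind | 4 | 1 | 8 MBq | 0.27 mSv | 0 | 5.4% |
| Scan limit binds, tracer limit does not | 5 | 1 | 10 MBq | 0.32 mSv | 0.05 mSv (18.5%) | 6.4% |
| Neither binds, V2 repeated in full | 5 | 2 | 10 MBq | 0.39 mSv | 0.12 mSv (44.4%) | 7.8% |

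The percentages are 0.05/0.27, 0.12/0.27, 0.27/5, 0.32/5 and 0.39/5.

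**Do the rules contradict each other?** The tracer and scan limits stand next to each other in the same paragraph, and both procedures belong to V2. Reaching 0.32 mSv means holding a re-entered subject to one limit and not the other. Applied evenly, the paragraph gives either 0.27 mSv (both bind) or 0.39 mSv (neither binds). Sections 4.6 and 6.5 say only that rescreening may happen. A permission used within a fixed limit is consistent with that limit, and no sentence obliges the site to re-enter anyone.

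**Effect on the analysis.** A subject who fails at V3 is not randomised, so is in none of the SAP's analysis sets (SAP Section 5.1.1). For a subject who did re-enter and had all scheduled assessments, the Day -1 baseline of SAP Section 5.2.2 would come from the V2 of the second pass. The ANCOVA is unaffected.

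**The case for a change.** The best case for acting is that nothing written down enforces the ceiling. Criterion 18 operates at 5 and 10 mSv and cannot hold anyone to 0.27 mSv. Criterion 19 carries no number. Section 6.5 names one group that cannot be screened again, drop-outs, and a subject already given tracer is not in it. Traceability is also less tidy than it might be: Section 15 records a link to the prior subject number in the eCRF, while Section 11 says screening failures are not entered there. The earlier dose may therefore be found only in source documents. One reconciling sentence would cost almost nothing.

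Part of this stands. The text is silent on this subject, and the ceiling rests on the wording of Section 1.3.1 alone. But that wording is explicit. The study is single-centre, so the site asked to re-enter the subject is the one that gave the earlier tracer, and Section 19 requires it to keep a record of everyone screened. All criteria, including 18 and 19, are checked again at a new V1.

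The shortage of 3 administrations for 4 assessments arises only if the site chooses a re-entry it is not required to make. The path is also narrow. The subject must pass the V2 re-check, when the alcohol, cotinine, drug, pregnancy and temperature checks are done, and fail the next morning. The cause must be judged temporary, and the subject must consent again, return and complete.

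**Conclusion.** This is a gap that a site following the protocol can fill sensibly. The stated maximum of 4 administrations and 0.27 mSv is arithmetically right for one pass. The rescreening text does not say how it applies after the V2 tracer, but a categorical limit and a discretionary permission can both be honoured. If the limit were nevertheless disregarded, the total would be 5 administrations, up to 10 MBq, and 0.32 to 0.39 mSv, which is 6.4% to 7.8% of 5 mSv.

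A clarifying sentence would alter no single-pass figure, no MCC estimate and no conclusion, so none is needed.

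This rests on Table 1's doses per procedure and on the maximum activity of 2 MBq (the target is 1 to 2 MBq). The documents give no basis for estimating how often a subject would fail between V2 and V3, and the submission to the radiation advisory committee is not among them, so any condition it sets on repeat administration is unknown.

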1.3.2 BENEFIT EVALUATION

This is a MCC study during which healthy subjects will be administered placebo propellants. Therefore, participation in this study does not imply any benefits for the subjects.

